Patients in the control condition will receive enhanced trauma center care as usual. Enhanced trauma center care as usual consists of nurse notification of control patients who screen into the study with high PTSD symptom levels. Patients in the intervention condition will receive a stepped collaborative care intervention targeting PTSD and related comorbidities. The intervention phase will begin with a one-day workshop training in care management, medication, MI, and CBT elements targeting PTSD and related comorbidity. These workshop trainings will occur on site at each of the 24 level I trauma center sites. The site PTSD intervention champion, as well as trauma surgical, nursing, psychiatric, social work, and other allied mental health providers who are already routinely delivering care at each of the sites will be invited to attend the workshop training. After the one-day workshop, the site will receive ongoing decision support facilitated supervision from the University of Washington study team.

Intent-to-treat outcome analyses will incorporate baseline patient reported outcome and trauma registry derived EHR data, as well as patient reported outcome assessment data from the 3-, 6-, and 12-months postinjury patient interviews. The investigation aims to determine if injured patients receiving the collaborative care intervention demonstrate significant reductions in PTSD symptoms when compared to control patients receiving care as usual. The study also aims to determine if the intervention patients, when compared to control patients, will demonstrate significant reductions in depressive symptoms and alcohol use problems, and improvements in physical function. The investigation is designed as an effectiveness-implementation hybrid that simultaneously aims to determine the effectiveness of the care management intervention while also assessing the potential utility of the implementation strategy.¹⁹¹ Thus, the investigative team will also use the RE-AIM framework and exploratory health economic analyses to better understand the processes of intervention implementation, as well as the resource implications for trauma care systems nationwide.

In the UH3 year 5 of the proposal, the results of the pragmatic trial will be presented at an American College of Surgeons' policy summit. A key focus of the summit will be discussion of the implications of trial results for screening and intervention for PTSD and comorbidity, clinical practice guidelines, and policy mandates. In particular, the study team will discuss findings that facilitate the implementation of real-time workflow integrated screening and intervention procedures for PTSD and comorbidity across trauma care systems nationally. The summit will be timed to optimally impact the next version of trauma center guidelines for PTSD and comorbidity.

B. Study Phases (see Figure 4)

Phase 1: Planning and start-up. In the start-up phase, the University of Washington (UW) study team has identified the 24 participating trauma center sites; potential wait list or "back-up sites" that could participate in the trial should initially contacted sites drop from the study have also been identified. At each potential site, the study team has identified three different types of "Champions", or individuals who have the background and experience at a trauma center to advocate for a particular component or element of the study protocol. The

three identified champions at each site are the trauma surgical champion, PTSD intervention champion and information technology champion. Also during the start-up phase, each site will be asked to assess their capacity for automated versus manual health record PTSD screening and to characterize their potential method for identifying injured patient cohorts and implementing the 10 domain PTSD risk factor screening elements.

Figure 4. UH2-UH3 Projected Timeline

Phase 2: Start-Up/Pre-randomization. Appropriate regulatory approvals (e.g., IRB, DSMB) will be obtained prior to initiation of this phase. Ten provider subjects will be consented and will complete a baseline organizational survey to assess their views and experiences of working in their respective trauma centers. Data quality assessments (e.g., whether 10 domain PTSD risk factor screening items are identified in the health record or from ward observation) will also begin during this phase.

Phase 3: Randomization. Randomization of the 24 trauma centers occurs during this phase.

Phase 4: Control phase initiation. Sites will be trained in the study protocol, recruitment procedure, consent process, and how to use the decision support tool recruitment modules. Recruitment of control patient subjects will begin following this training. Data quality assessment procedures and baseline standardized patient interviews with care manager provider subjects will also occur in this phase.

Phase 5: Follow-up outcome assessments. Follow-up interviewer training will begin prior to the initiation of this phase. The 3-, 6- and 12-month, blinded follow-up interviews will begin and continue ongoing throughout this phase.

Phase 6: Intervention phase initiation. Recruitment of control patient subjects will end at each site based upon the wave they are assigned in the stepped wedge design. The UW intervention study team members will conduct a one-day intervention training workshop at each site at this time. Following this training, each site begins recruitment of intervention patient subjects and their care manager subjects begin charting notes in the decision support tool and have regular supervision with the UW study team. Intervention feedback and coaching will occur during this phase. Standardized patient sessions continue during this phase. Data quality assessment procedures will also continue at each site in this phase. All provider subjects will be asked to complete another organizational survey, after this phase is completed.

Phase 7: Final study procedures. Final data cleaning and analyses will be conducted in this phase. Manuscript preparation and the end of study policy summit will occur in this phase. The UW study team will coordinate with the American College of Surgeons' Committee on Trauma, as well as other stakeholders to hold a policy summit.

C. Site Eligibility and Recruitment

Over the course of the start-up phase, the TSOS study team has recruited the 24 trauma center sites that will

participate in the trial. The goal of the selection process was to recruit 24 level I trauma centers nationally that would be capable of efficiently implementing the study procedures. The study team sent notification emails and/or contacted by telephone all US level I trauma centers (Figure 5). Responding centers were asked questions about current PTSD screening and intervention practices; the study excluded the less than 10% of sites nationally that were already routinely screening and intervening for PTSD and related comorbidity. Pediatric specialty trauma centers were also excluded from the investigation, as elements of the intervention (e.g., the administration of psychopharmacological agents targeting PTSD) are less well established for patients under the age of 18.

With the exception of pediatric trauma center specialty status, the organizational characteristics of the 24 participating sites does not substantially differ from the characteristics of all US level I trauma centers potentially eligible for the study (Table 3). Site level generalizability/reach is an important aim of the investigation as it aims to influence American College of Surgeons' policy for PTSD and comorbidity screening and intervention for all trauma centers nationwide (see the RE-AIM investigation implementation assessments in the Statistical and Data Analysis Plan section). Potential sites were also required to identify three champions to assist with study implementation; the trauma surgical champion, the PTSD intervention champion, and the information technology champion (Table 4).

Table 3. Organizational Characteristics of TSOS study versus all US level I trauma centers				
Characteristic	UH3 TC N=24 N(%)	Other TCs N=198 N(%) P	
Region of country			0.40	
Midwest	7(29.2)	64(32.3)		
South / Southeast	4(16.7)	30(15.2)		
Northeast /East	5(20.8)	63(31.8)		
West	4(16.7)	28(14.1)		
Central	4(16.7)	13(6.6)		
Rural status	3(12.5)	24(12.1)	1.0	
Population served			0.03	
Adult	7(29.2)	92(46.5)		
Adult & pediatrics	17(70.8)	82(41.4)		
Pediatrics	0(0.0)	23(11.6)		
Missing	0(0.0)	1(0.5)		
Teaching hospital	23(95.8)	162(81.8)	0.14	
Council of teaching hospitals	22(91.7)	143(72.2)	0.04	
University affiliation	24(100.0)	189(95.5)	0.60	
	М	edian(IQR)		
Number of interns/residents	327(282)	224(297)	0.11	
Number of hospital beds	575(296)	534(318)	0.40	
Number of inpatient admits	26971(16311)	25699(14978)	0.28	

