The pragmatic trial demonstration project is designed to test the implementation of efficient, high quality screening and intervention for PTSD and comorbidities across 24 US level I trauma center sites. The investigation will employ a stepped wedge cluster randomized design. In the stepped wedge design, level I trauma center sites are randomized sequentially to initiate the intervention. In the UH3 implementation phase, after IRB approval is obtained, each of the 24 trauma center sites will be randomized to one of four waves. All sites will begin with control patient recruitment and each wave is assigned a specific proportion of control and intervention patient recruitment. Wave one recruits 8 control and 32 intervention patients, wave two recruits 16 control and 24 intervention, wave three recruits 24 control and 16 intervention, and wave four recruits 32 control and 8 intervention patients. The demonstration project aims to recruit 960 patients, 40 at each trauma center site.

A routine trauma center provider, the site PTSD intervention champion, will be selected to orchestrate screening and intervention procedures. All sites will work with the study team to implement an EHR initial PTSD risk evaluation. Patients identified by EHR evaluation as at-risk for high early PTSD symptom levels (i.e., a score of \geq 3 risk domains positive) will then be formally screened for study entry with the patient reported outcome measure, the PTSD Checklist. Formal study cohort definition occurs with the PTSD Checklist; patients scoring \geq 35 on the PTSD Checklist will be followed in the longitudinal portion of the investigation.

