Patient identification and recruitment procedures described below were successfully piloted during the the UH2 start-up phase of the project. PTSD interventionist and other providers will identify potential patient subjects by reviewing inpatient rosters and identifying individuals who are most likely to have PTSD using the UW study team's validated PTSD screening algorithm further described below. Care manager subjects will then approach potential patient subjects about the study.

1. Potential patient subjects are identified by searching health records at each site for inpatients brought into the hospital for a traumatic injury. In order to review those records for this purpose, the study team will apply for and receive a waiver of consent and a waiver of HIPAA authorization.

2. In order to enhance the efficiency of trauma care system PTSD case finding, the study team has developed and implemented a 10 domain PTSD risk factor screen (Appendix 5).⁴⁹ The 10 domains used for screening are: 1) Female gender, 2) Non-white race/ethnicity, 3) Intentional injury, 4) Public or Veterans insurance status, 5) Intensive Care Unit (ICU) admission, 6) Previous hospitalizations 7) Substance use, 8) Tobacco use, 9) Evidence of PTSD diagnosis, 10) Other mental health diagnosis.

3. The PTSD screening evaluation can either be applied in an automated or manual format. The automated form of the evaluation can be programmed into the hospital computing system, while the manual form of the evaluation involves screening individual health records for the 10 PTSD risk factor domains. At both automated and manual sites that select the manual screening, UW study team members will train PTSD intervention care manager subjects to adhere to the chart abstraction checklists developed and validated by the UW study team (see also the Data Quality Assurance and Harmonization section).

4. Each day the PTSD interventionist will oversee a hospital-based review for admitted injured patients. The review will aggregate data from the 10 PTSD risk factor domains. Patients with higher scores on the evaluation (i.e., more positive risk elements) will be prioritized for approach for formal PTSD symptom assessment with the PTSD Checklist. Providers will identify potential patient subjects who meet the criteria of

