The care management intervention elements are distilled from manualized procedures derived from the study team's previous intervention trials (Appendix 7). The delivery of specific elements will be dependent on care manager time allocation and patient subject intensity of symptoms. In the protocol, care management will occur up to six months after the injury. It is anticipated that the care manager will spend approximately 2-4 hours working on intervention and treatment linkage for each intervention patient. The care manager will attempt to meet all intervention patients during their trauma center or emergency department stay. During this meeting, the care manager will begin to elicit and target for improvement each patient's unique constellation of posttraumatic concerns. This will help to enhance initial treatment engagement and therapeutic alliance. The care manager will give the patients their hospital contact number and encourage calls for spontaneous questions and concerns. The care manager will also elicit treatment preferences (e.g., CBT only, medication only, combined treatment) for PTSD and comorbidity and will schedule ongoing times to meet/call the patients during the initial days and weeks post-injury. Whenever possible, patients' family members will be integrated

into treatment planning and longitudinal care. The care manager will elicit information regarding patients' plans for physical and mental health care follow-up, and will inquire about whether or not the patients have a primary care provider (PCP). During caseload supervision, this information will be relayed back to the supervising UW study team members. After team discussion, the care manager subject will discuss treatment options with the patient and come to a shared decision about the initial treatment plan with the patient, their family members, and providers.

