1. Injury cohort definition. Appendix 9 has the study team definition of injury in terms of ICD codes and natural language indicators. These definitions will be applied by all sites. These definitions will be provided to each site during the pre-randomization phase. The study team will then have in-depth conversations with the IT champions and/or PTSD intervention champions at each site to identify the procedures used to generate the daily list of inpatients based on the definition. In these conversations, the study team will determine how the list of injured inpatients will be generated, what the list will contain, whether there needs to be manual editing of the list, and what criteria or risk factors will need to be gathered directly from the EHR. The study team also determines whether patients on the daily list include inpatients from a variety of services in order to increase generalizability. These services will include general surgery, orthopedics, neurosurgery, ENT/Maxillofacial, trauma ICU, and ER admissions

for \geq 24 hours. Services available for the cohort will be noted for each site. This information will be incorporated into the workflow manual individualized for each site. These procedures have been piloted during the UH2 phase of the protocol and manuals and worksheet guides for these procedures have been refined and are included (Appendix 9).

Exclusion criteria. The study recruitment consort (Figure 6) and Appendix 9 define exclusion criteria. At
each hospital, these criteria can be addressed in several ways, depending upon the capacity of the
EHR and its programming potential. The fully automated sites will eliminate inpatients from the injury
cohort daily list within the EHR query or using spreadsheet macros and those excluded individuals may

or may not be visible to the recruiter. In contrast, sites may use the manual abstraction procedure in which the first group of patients are chosen, and the exclusion criteria are examined in the EHR individually by the recruiter. As soon as an exclusion is identified, the recruiter would go on and choose the next inpatient on the list for further examination. Some sites will use a combination of automated and manual exclusion procedures. These criteria can be determined from the EHR, by patient observation, or by patient interview.

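### Recruiters know which condition is open and treat only intervention-phase enrolees, yet the order of approach is loosely specified, so patient selection can differ between phases within a site

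*Combined protocol and SAP*

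**What the plan says.** **Allocation.** Section A, Design Overview, randomizes sites to four waves with fixed quotas: "Wave one recruits 8 control and 32 intervention patients, wave two recruits 16 control and 24 intervention", then "wave three recruits 24 control and 16 intervention, and wave four recruits 32 control and 8 intervention patients". The order of conditions is the same everywhere: "All sites will begin with control patient recruitment and each wave is assigned a specific proportion of control and intervention patient recruitment". In Study Phases, randomization (Phase 3) comes before control recruitment (Phase 4). Phase 6 ends the control period by wave: "Recruitment of control patient subjects will end at each site based upon the wave they are assigned in the stepped wedge design". The one-day workshop at the site comes next, and intervention recruitment follows it.

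**Who recruits and who treats.** Section E, on patient eligibility and recruitment, says: "Care manager subjects will then approach potential patient subjects about the study". Site recruiters are also trained to give the PTSD Checklist, on which a score of 35 or more decides entry to the followed cohort. After the workshop the care managers deliver the intervention for up to six months, and it is expected that "the care manager will spend approximately 2-4 hours working on intervention and treatment linkage for each intervention patient". The enhanced part of control care is a nurse notification, which intervention patients receive too.

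**Order of approach.** Section E requires at least 3 positive risk domains and gives priority to higher scores. It also says that recruitment will differ between sites, including in how many patients are selected each day. It states no consecutive or random order and no tie-break.

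**What is hidden from recruiters.** In the control phase, only the intervention elements of the decision support tool are hidden. The phase itself is not.

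**The concern.** Sites are randomized, but patients are enrolled afterwards by staff who know what each enrolee will receive. In the control phase an enrolee brings the recruiter little further work. In the intervention phase the same person takes on several hours of care. That difference could affect who is approached or encouraged to join, for example by favouring patients who seem engaged. It could also work the other way, toward patients seen as most in need.

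Randomizing sites to waves does not protect against this, because the selection arises within a site, between its two phases. Model A adjusts for period, baseline Checklist score and a site effect. Any other prognostic difference between control-phase and intervention-phase enrolees would be read as treatment effect.

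**Working it through.** **Inputs.** 24 sites; 5 enrolment periods (t = 0 to 4, Model C notation); 30 completers per site after 25% attrition, so 30/5 = 6 per site-period; ICC 0.02; autocorrelation 0.7; alpha 0.05; power 80%; Checklist SD 15 (Tables 10 and 11). Assumed: 6 sites per wave, a two-sided test, total variance 1.

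**1. Reproduce the plan's figure.** The Hussey–Hughes stepped-wedge variance is

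Var = I·s²(s² + T·τ²) / [(I·U − W)s² + (U² + I·T·U − T·W − I·V)τ²],

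with I = 24, T = 5, s² = 0.98/6 = 0.1633, τ² = 0.02, U = 60, W = 1080, V = 180.

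- Numerator: 24 × 0.1633 × 0.2633 = 1.032.
- Denominator: 360 × 0.1633 + 1080 × 0.02 = 80.4.
- Var = 0.01284. Multiplying by 1 − 0.7² = 0.51 for baseline adjustment gives 0.00655, so SE = 0.081.
- Detectable effect: 2.80 × 0.081 = 0.227.

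The same steps at ICC 0.005, 0.010 and 0.030 give 0.216, 0.220 and 0.231. All four values match Table 10.

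**2. Pass-through.** Suppose intervention-phase enrolees differ in expected outcome by d, beyond what the baseline score explains. The shift is d times the condition indicator, which is already a column of Model A. The expected estimate of β6 is therefore the true effect plus d, whatever the period terms or ICC.

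**3. False-positive rate under no true effect.** Rejection probability = Φ(d/0.081 − 1.96) + Φ(−d/0.081 − 1.96). The shifts are assumptions.

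| Assumed d (SD) | Checklist points (×15) | Share of 0.227 | Rejection |
|---|---|---|---|
| 0 | 0 | 0% | 5% |
| 0.05 | 0.75 | 22% | 9.5% |
| 0.10 | 1.5 | 44% | 23.5% |

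A shift the other way would hide benefit. With a true effect of 0.227 and an opposing shift of 0.10, power is Φ(0.127/0.081 − 1.96) = Φ(−0.39), or about 35% instead of 80%.

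**4. Measured and unmeasured imbalance.** Model A was simulated under the null, with 2,000 runs per scenario and variance components taken as known.

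- 0.2 SD imbalance in the baseline score only: bias about 0, rejection 0.06.
- Unmeasured factor worth 0.1 SD on the outcome: bias 0.10, rejection 0.25.
- Unmeasured factor worth 0.2 SD: bias 0.20, rejection 0.71.

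**5. Holding a particular patient for the switch.** Patients within 1 to 4 enrolments either side of the switch number 24 × 2 × 1 = 48 to 24 × 2 × 4 = 192, or 5% to 20% of 960. Suppose one of the 8 patients enrolled (40/5) in each cell next to the switch is affected at every site. The last control cell then moves by −gap/8 and the first intervention cell by +gap/8. Projecting these cell means on period and condition by generalized least squares moves β6 by 0.177 × gap. A gap of 0.5 SD gives about 0.09 SD.

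**The case against.** **Steering between conditions.** A reader might infer that allocation is predictable throughout and that patients can be steered freely between conditions. The documents do not support that. Only one condition is open at a site at a time, the pool is current inpatients reviewed daily, and a workshop separates the phases. Holding a particular patient is plausible only near the switch. The 0.09 SD illustration also needs the same swap in the same direction at all 24 sites, and a gap that the baseline score does not capture; 0.5 SD is 0.5/√0.51 = 0.70 of the residual SD.

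**Free choice from the list.** It is tempting to read the data-quality section, where "sites may use the manual abstraction procedure in which the first group of patients are chosen" and "the recruiter would go on and choose the next inpatient on the list for further examination", as free choice of whom to approach. In context it describes checking exclusion criteria chart by chart down a list. The gap in the approach rule itself is narrower: no tie-break, no required order among eligible patients, and varying daily volume.

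**Existing safeguards.** Several narrow the problem. Two working contacts are required before consent, with no distinction by phase, which limits differences in reachability. Drift checks are made in each phase, Table 7 follows the Checklist-positive rate in both, and non-consenter data arrive weekly. None settles the point:

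- Drift checks test concordance on cohort definition and risk domains, not who was approached.
- The registry comparison sets enrolled against eligible patients and is not stated to be made by condition.
- The demographic tests are aimed at bias across clusters; their interactions with treatment ask whether the effect varies, not whether the phases enrolled comparable patients.
- Blinded follow-up protects outcome measurement, not selection.

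**Inherent to the design.** An open phase is common in stepped-wedge trials that recruit after randomization, and the plan gives reasons for the design. That stands. The order of approach, however, can still be fixed.

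**Missing text.** When sites learn their wave cannot be judged: part of the text after Table 3, Figure 16 and the appendices with the workflow manuals were not available. The point does not depend on it, since the current phase is evident to staff in any case.

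**Conclusion.** The concern holds as a risk of differential selection between phases within a site. It rests on three facts in the protocol: the open condition is known at recruitment, the approaching care managers carry the treatment workload in one phase only, and the approach rule leaves room for judgment.

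Any resulting difference in unmeasured prognosis enters β6 in full, and shifts that are modest beside the detectable effect would matter. The shift sizes are assumptions that no passage supports or excludes. The direction is also unknown, since favouring engaged patients and favouring needy patients could pull β6 opposite ways and partly cancel. The documents therefore do not show that the trial is biased, only that the recruitment rule leaves this route open and that no stated check would clearly detect it.

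**What to change.** **Main change, identical in both phases.**

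- Each day, rank the patients with 3 or more positive domains by risk score, breaking ties with a random number generated in the decision support tool or daily spreadsheet.
- The recruiter works down that list and logs a coded reason for every patient passed over.
- Report numbers and rates screened, approached, consented and Checklist-positive by condition.

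**Secondary, partial measure.** If sites are told their wave at randomization, have the coordinating center hold it back until the workshop must be scheduled. This limits anticipation of the switch. It cannot conceal the phase once the workshop has taken place.

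**Cost.** A change to the recruitment procedure, a sort column and a reason code, built on the existing daily list and weekly non-consenter transfer, with no extra staff. Recruiters lose some scheduling flexibility, and some patients will be logged as missed because they are discharged before their turn.
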